1.13. Target Population

All children between 6 and 15 years of age (excluding upper limit) in whom parasites are detected in the blood, lymph or CSF will be included in the study. Only children who are able to swallow the tablets will be eligible for the study.

Given the limited number of children with HAT, all children in whom parasites are detected in the blood, lymph or CSF will be included, regardless of the stage of the disease.

The stages are defined as follows:

Patients with stage-1 HAT

- Trypanosomes in blood and/or lymph
- No trypanosomes in CSF
- CSF WBC ≤ 5/µL

Patients with early stage-2 HAT

- Trypanosomes in blood and/or lymph
- No trypanosomes in CSF
- CSF WBC > $5/\mu$ L and $\leq 20/\mu$ L

Patients with late stage-2 HAT

• Trypanosomes in blood and/or lymph

and

CSF WBC > 20/µL

Or

• Trypanosomes in CSF

An informed consent form, signed by the legal representative, i.e. one of the parents or the legal representative, will be collected for each child, and assent from the child will be collected in the presence of an impartial witness (see Section 14 Ethical Considerations; p 70).

2. Study Objectives and Endpoints

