2.1.2. Secondary Objectives

- To verify whether the success rate varies depending on the stage of the disease; if the success rate is significantly different between the 3 strata, to show that the rate is greater than 80% and compatible with the historical success rate reported with NECT in patients with stage-2 HAT and with pentamidine in patients with stage-1 HAT.
- To verify whether the success rate of treatment with fexinidazole varies depending on the WBC count in the CSF prior to treatment initiation.
- To study changes in the success rate over time.

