9.8.3. Secondary Efficacy Analyses

- The secondary analysis will be performed on the success rate at month 18.
- determine whether the success rate of treatment with fexinidazole varies depending on the stage of the disease, i.e. stage 1 versus early stage 2 versus late stage 2, using a Fisher exact test to compare the rates observed with the 3 different stages.

If the difference between the 3 stages is significant, then the exact 95% CI of each success rate at 12 months will be calculated, and the stage that is responsible for the heterogeneity will be identified. The stage responsible for the heterogeneity will be separated from the other 2 stages, and the lower limit of the 95% CI of each of the 2 subgroups will be compared to the limit of 75%, which is slight higher than the success rate of melarsoprol at 12 months. A limit lower than 80%, i.e. 75% instead of 80%, was chosen because the sample size in each subgroup will be smaller, which will have an impact on the statistical power of each comparison. The upper limit of the CI of the success rate in patients with stage-1 HAT should be consistent with (greater than or equal to) the rate of 93%, which is the

historical success rate of pentamidine (61). The upper limit of the CI of the success rate in patients with stage-2 HAT should be consistent with the rate of 94%, which is the historical success rate of NECT.

- The correlation between the success rate and the WBC count in the CSF will be estimated using a logistic regression. The WBC count will be a quantitative covariate. Another analysis will be performed using a logistic regression with a random intercept to take into account the centre effect. A trend test will also be performed using the Bartholomew's test. Another analysis will be performed after pooling patients with late stage-2 HAT treated with fexinidazole in the pivotal study with patients in this study. The correlation between the success rate and the baseline WBC count will be adjusted with a logistic regression model using the centre as covariate.
- The time-course of the cumulative rate of definitive failure (from the start
 of treatment to the definitive failure) will be estimated using the KaplanMeier method, and patients lost to follow-up will be considered as
 censures. The success rate at each timepoint will be estimated and
 compared using a Cochran Q-test. The logistic model for repeated
 measures (Glimmix procedure in SAS[®]) will be used to test the time effect

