 adjusted by centre.

Data on patients with stage-1 and early stage-2 HAT in the DNDiHATFEX005 study will also be pooled. A logistic model with success at 12 months as the response and stage as covariate, as well as the study, will be used. The main results will concern the homogeneity of the success rates for the various stages. If there is heterogeneity, the success rate in patients with stage-1 HAT should not be lower than the success rate in patients with stage-2 HAT.

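### The pooled CSF WBC model names centre but not study as a covariate, so a child-adult difference in cure can be partly read as, or can mask, a WBC effect

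*Protocol*

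**What the plan says.** One secondary objective (Protocol 2.1.2) is "To verify whether the success rate of treatment with fexinidazole varies depending on the WBC count in the CSF prior to treatment initiation".

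Section 9.8.3 serves it with several analyses. Three are described before any pooling is mentioned: a logistic regression ("The WBC count will be a quantitative covariate"), the same with a random intercept for centre, and Bartholomew's trend test. A pooled analysis follows: "Another analysis will be performed after pooling patients with late stage-2 HAT treated with fexinidazole in the pivotal study with patients in this study". In it, the relation between success and baseline WBC "will be adjusted with a logistic regression model using the centre as covariate". No study, age-group or stage term is named, and no timepoint is given for success.

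The same section then describes a second pooling, with the stage-1 and early stage-2 patients of DNDiHATFEX005. There the adjustment is fuller: "A logistic model with success at 12 months as the response and stage as covariate, as well as the study, will be used".

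Four other statements matter here:
- Section 1.13 enrols children "regardless of the stage of the disease", and section 4.2 leaves the strata self-weighted.
- Late stage 2 means CSF WBC above 20/µL or trypanosomes in the CSF (section 1.13).
- The study runs at the pivotal study's sites (section 3).
- The children are under 15 years (section 1.13). The pivotal patients described in section 1.11 were aged 15 to 71.

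**The concern.** In the pooled data the adults add almost only high WBC values, while the children supply nearly all the low ones. WBC is thus tied to study, and study coincides with age group and largely with dosing band. A model with WBC and centre cannot tell the two apart, because every centre may hold both children and adults. If children and adults differ in cure for any reason, part of that difference passes into the WBC coefficient. Depending on its direction, it creates a gradient or hides one.

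The question bears on the stated aim of treating all patients without CSF-based staging (section 1.12). A false gradient would argue wrongly for staging, and a masked one wrongly against it. The protocol itself treats the child-adult comparison as open, since section 1.12 plans to compare results between the two studies.

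**Working it through.** **The plan's own figure.** The protocol gives none for this analysis. Its primary design figure reproduces: with 125 patients and at least 109 successes, exact power is 0.978 at 92% (97.5% stated) and alpha is 0.0243. That test is not touched by this point.

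**Inputs from the protocol**
- Children: 125 (section 9.1).
- Adults on fexinidazole: about 125 as of November 2013 (section 1.10); the final number is not given.
- Expected success: 92% here at 12 months, 89% in the pivotal study at 18 months, and a stated gain of 1.2% for the earlier timepoint (section 9.8.1). On one timepoint the adult figure is 89 + 1.2 = 90.2%, a gap of 92 − 90.2 = 1.8 points.

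**Assumptions**
- Stage mix of the children (stage 1 / early 2 / late 2): 30/15/55% or 50/20/30%.
- 125 or 250 adults.
- Late stage-2 WBC equal to 20 plus a lognormal value with median 120 and log SD 1.0. This ignores late stage-2 patients who qualify by CSF trypanosomes with a WBC of 20 or less.
- Eight shared centres, and no true WBC effect in either group.

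**Mechanism by arithmetic.** Let n be the number of late stage-2 children, m the number of adults, and c and a their success rates. Success is c at low WBC and (n·c + m·a)/(n + m) at high WBC.
- 30/15/55 mix, n = 68.75, m = 125, 97% v 89%: (66.69 + 111.25)/193.75 = 91.8%, against 97% at low WBC.
- 50/20/30 mix, n = 37.5, m = 250, 97% v 89%: (36.375 + 222.5)/287.5 = 90.0%, against 97%.
- 50/20/30 mix, n = 37.5, m = 250, 92% v 90.2%: (34.5 + 225.5)/287.5 = 90.4%, against 92%.

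An apparent WBC gradient arises with no WBC effect in either group, and it is small at the protocol's own rates.

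**Simulation.** Logistic model: logit P(success) = centre + β·log10(WBC + 1), with and without a study term. 600 runs per setting, two-sided 5%. Ranges span both mixes and both adult numbers. OR is the median odds ratio per tenfold WBC.

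| Success, children v adults | False positives, WBC + centre | OR | False positives, study added |
|---|---|---|---|
| 92% v 92% | 4–6% | 0.99–1.02 | 4–6% |
| 92% v 90.2% | 4–6% | 0.90–0.93 | 3–6% |
| 95% v 90% | 7–18% | 0.70–0.75 | 3–5% |
| 97% v 89% | 13–46% | 0.53–0.63 | 4–5% |
| 98% v 90% | 16–52% | 0.47–0.59 | 4–5% |

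At 97% v 89%, the 30/15/55 mix gives 13 to 20% and the 50/20/30 mix 35 to 46%. With the study term, the OR there is 0.98 to 1.01. The Monte Carlo standard error at a 5% rate is √(0.05 × 0.95/600) = 0.9 points.

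**Sensitivity**
- Raw WBC scale: at most about 12% false positives in any setting.
- Children limited to late stage 2 (250 adults, 55% of children late): 5 to 7%, OR 0.95 to 0.97 without a study term.
- Reverse direction, 90% in children and 95% in adults: a spurious effect of opposite sign in 11 to 19%. That run left centre out, so it shows direction more than size.

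**The case against.** The strongest case against is that little rests on this model. The children-only regressions and the trend test address the same objective, cover all stages and cannot be confounded by study. The Fisher test across stages and the DNDiHATFEX005 pooling, which has a study term, also speak to staging. The pooled fit carries no decision rule. A spurious pooled slope would stand beside unconfounded ones. This stands, and it limits the importance of the point.

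Three further arguments limit the size, and they stand too. Bias needs a real child-adult difference, and even then it is partial, because late stage-2 children overlap adults in WBC. The protocol's expected rates give about nominal error. The WBC scale is not stated, and section 1.2 says that children seem to progress faster to stage 2, which may mean fewer low values than assumed here.

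The children pooled could also be meant as late stage 2 only, in which case nearly all the bias disappears. The text does not say so, and the ambiguity itself needs resolving.

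Lastly, covariate lists are often completed in the SAP. Here, however, the protocol names the adjustment ("adjusted with a logistic regression model using the centre as covariate") and, for the other pooling, adds the study ("stage as covariate, as well as the study, will be used"). An SAP that follows the protocol as written would inherit the gap.

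A reader might infer that the pooled model will report a false WBC effect, or that the WBC objective is compromised. The documents support neither: they establish no child-adult difference in cure, and the objective has analyses free of this problem.

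**Conclusion.** The point holds as a cheap improvement to a supportive secondary analysis. As written, the pooled model confounds WBC with study and names a covariate that cannot separate them, although the neighbouring pooled model names the right one. The consequence is conditional: a true child-adult difference in cure can be partly read as, or can mask, a WBC effect.

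Its size depends on the stage mix, the WBC scale and the true difference, none of which the protocol fixes. It is negligible at a gap of 1.8 points, modest at 5 points, and substantial on the log scale at 8 points, especially if most children are below late stage 2. These figures illustrate the mechanism and do not predict the trial's result.

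**What to change.** In section 9.8.3, or in the SAP:
1. Add study as a fixed effect beside centre in the pooled WBC model, as the DNDiHATFEX005 pooling already does.
2. Name success at 12 months as the response in both studies. The pivotal rate is set at 18 months, so mixing timepoints would widen the expected gap from 1.8 to 92 − 89 = 3 points.
3. State whether the pooled children are of all stages or late stage 2 only.

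A fit limited to late stage-2 patients of both studies, with a WBC-by-study term, is optional. It would show whether the slopes agree where the WBC ranges overlap.

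The change takes a sentence or two and one model term. The cost is a wider interval for the WBC slope, which is the appropriate one, since the adults carry almost no information at low WBC.

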2.2. Study Endpoints

2.2.1. Primary Efficacy Endpoint

The primary efficacy endpoint is the outcome, i.e. success or failure, observed at the test-of-cure (TOC) visit, 12 months after the end of treatment (EOT).

Success at 12 months, adapted from WHO criteria (54), is defined as:

- Patient cured, i.e.:
 - o patient alive,
 - AND no evidence of trypanosomes in any bodily fluid,
 - o AND CSF WBC ≤ 20/μL.

A patient with no evidence of trypanosomes in any bodily fluid, but with CSF WBC > $20/\mu$ L, or who, in the opinion of the Investigator, requires rescue treatment will be considered as a probable relapse.

Patients lost to follow-up and retrieved after 12 months or patients who refuse to undergo lumbar puncture at 12 months will be considered as patients probably cured, i.e. successes, if they have no clinical signs or symptoms suggestive of HAT or if their symptoms can be clearly attributed to another aetiology, provided that the outcome was favourable at the last available assessment of HAT (6-month visit or subsequent unscheduled visit). If a patient is not assessed, i.e. has no lumbar puncture, at 12 months, but has a lumbar puncture or physical examination subsequently or at 18 months, the outcome at the latter visit will prevail over that at 12 months.

Patients who die due to any cause, patients lost to follow-up and not retrieved, and patients who refuse to undergo lumbar puncture at 12 months and whose clinical outcome had previously been assessed as unfavourable, i.e. probable relapse, will be considered as failures.

The prinicipal visit for assessment of the efficacy endpoint, i.e. success or failure, was set at 12 months after the EOT because the relapse rate between 12 and 18 months is very low and highly consistent across the various treatments administered to patients with stage-2 HAT (historical data). The success rate for melarsoprol was 74.84% at 12 months and 73.71% at 18 months, i.e. a relapse rate of 1.1% (n=3477), (61). The success rate for effornithine was 90.3% at 12 months and 89.1% at 18 months, i.e. a relapse rate of 1.2% (n=743), (61). The relapse rate for NECT was 1.4% (n=143) between 12 and 18 months after the EOT (43). Consequently, the overall relapse rate between 12 and 18 months after the EOT is around 1.2% for patients with stage-2 HAT, regardless of the treatment. The consistency of the findings suggests that the success rate at 12 months is predictive of the success rate at 18 months.

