2.2.2. Secondary Endpoints

Efficacy

Result (success or failure) at each visit from the end of treatment to month 18.

Safety Endpoints

Adverse events (AEs) will be graded according to the Common Toxicity Criteria for Adverse Events (CTCAE) of the National Cancer Institute (NCI), Version 4.03.

- Occurrence of any AEs grade ≥ 3, including laboratory abnormalities, during the observation period;
- Occurrence of any AEs, at any grade, during the observation period;
- Occurrence of any treatment-related AEs (grade ≥ 3 and any grade) during the observation period;
- Occurrence of any SAEs between the first intake of the IP and the end of the follow-up period (18 months).

ECG abnormalities with no clinical symptoms will not be reported as AEs. ECG changes will be analysed separately. If cardiac symptoms are present, information collected from ECG will be recorded in the eCRF.

PK Endpoints

Concentrations of fexinidazole, M1 and M2 in whole blood and CSF, and PK parameters derived from a population PK model.

 Samples of whole blood will be collected using dry blood spot (DBS) testing on venous puncture at the following timepoints:

- On Day 10, 3 hours and 7 hours 15 minutes after the last intake of fexinidazole;
- o On Day 11, i.e. 24 hours after the last intake of fexinidazole;
- o On Day 12, i.e. 48 hours after the last intake of fexinidazole.
- Lumbar puncture will be performed at Day 11, 24 hours after intake of fexinidazole for the EOT efficacy assessment in the first 30 patients. A dry CSF spot will be collected at the same time for PK analyses in the first 30 patients.

ECG Endpoints

Triplicate ECG tracings will be recorded at 2-minute intervals to assess QT interval at the following timepoints:

- At baseline
- On Day 4, 4 hours (H4) after intake of fexinidazole, on Day 4 H23 and on Day 10 two to three hours after intake of fexinidazole.

Triplicate ECGs and a safety ECG will be collected for different purposes and will be analysed separately (see Section 6.3.2 ECG Recordings; p 46).

3. Study Design

This is an open-label, multicentre, Phase II/III study. The study will be a plug-in to the pivotal study, DNDiFEX004, and will be performed at the same sites.

4. Selection of Study Population

To be eligible for inclusion in the study, patients must fulfil all of the inclusion criteria and none of the exclusion criteria.

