5.9. Rescue Treatment

Patients who show no clinical response to treatment at the EOT visit, as well as patients with evidence of relapse, i.e. *T.b. gambiense* found in any bodily fluid, or of probable relapse at any time during follow-up will receive NECT, an alternative treatment for HAT, as per usual practice in the investigational centre.

The definition of probable relapse disclosed at the 6-month, 12-month or 18month follow-up visit is provided in Table 1.

Rescue treatment for HAT will not be recorded in the "Concomitant Treatment" section of the eCRF, but will be recorded as a comment on the "End of Study" page with the date of treatment start.

Table 1 – Clinical Management of Patients

Visit	Ideal timing of visit after end of treatment	Success	Probabale success	Probable failure	Proven failure
24 hours after EOT	Within 2 days	• Patient alive with no evidence of trypanosomes in any bodily fluid (54)			 Evidence of trypanosomes in any bodily fluid
3 months	3 months ± 1 week	 Patient alive with no evidence of trypanosomes in any bodily fluid (no lumbar puncture at 3 months unless Investigator suspects a relapse) 	 Any reason leading the Investigator to request an additional follow-up visit 	 Signs or symptoms suggestive of HAT and of treatment failure leading to use of rescue treatment 	 Evidence of trypanosomes in any bodily fluid
6 months	6 months ± 2 weeks	 Patient alive with no evidence of trypanosomes in any bodily fluid and CSF WBC ≤ 20/µL 	 CSF WBC between 20 and 50/µL and additional follow-up visit requested within 1 to 3 months Any reason leading the Investigator to request an additional follow-up visit 	 CSF WBC ≥ 50/µL (36) Neurological signs or symptoms leading to use of rescue treatment 	 Evidence of trypanosomes in any bodily fluid
12 months	12 months ± 4 weeks	 Patient alive with no evidence of trypanosomes in any bodily fluid and CSF WBC ≤ 20/µL 	 CSF WBC > 20/µL and clinically non-significant increase as compared to previous value(s) CSF WBC > 20/µL and < 50/µL and reduced as compared to previous value(s) Any reason leading the Investigator to request an additional follow-up visit within 1 to 3 months 	 CSF WBC ≥ 50/µL Signs or symptoms suggestive of HAT and of treatment failure leading to use of rescue treatment 	 Evidence of trypanosomes in any bodily fluid

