18 months	18 months ± 4 weeks	 Patient alive with no evidence of trypanosomes in any bodily fluid and CSF WBC ≤ 20/µL Patient with no signs of HAT who refuses to undergo lumbar puncture and who, in the opinion of the Investigator, does not require rescue treatment or an additional follow-up visit 	Any reason leading the Investigator to request an additional follow-up visit within 1 to 3 months	 CSF WBC > 20/µL Signs or symptoms suggestive of HAT and of treatment failure leading to use of rescue treatment 	 Evidence of trypanosomes in any bodily fluid

An uncertain outcome may be a discrepancy between the clinical picture and the laboratory findings, or any situation that leads the Investigator and the study team to consider that an additional follow-up visit is required to decide whether or not to provide rescue treatment.

6. Schedule of Study Procedures and Assessments

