9.1. Sample Size Determination

Determination of the sample size was based on the primary analysis (see Section 9.8.1 Primary Efficacy Analysis, p 61). With a sample size of 125 patients, the probability of rejecting H_{0A} ($\pi \le 0.8$) is 97.5% if the true success rate is 92% with a one-sided type-I error of 0.025. The probability of rejecting H_{0B} ($\pi \ge 0.92$) is also 97.5% if the true success rate is 80% with a one-sided type-I error of 0.025. The statistical power achieved is slightly higher than the desired power, and the alpha value obtained is slightly lower than the desired value, due to the discrete distribution of the population. The sample size may be 126 patients who received at least one dose of fexinidazole if two patients are recruited simultaneously at the time of study discontinuation. If the sample size exceeds 126 patients, there is a risk of simultaneously rejecting both H_{0A} and H_{0B}. The sample size should not be less than 125 in order to avoid the risk of not rejecting either hypothesis.

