9.8. Efficacy Analysis

9.8.1. Primary Efficacy Analysis

Primary Efficacy Endpoint

The primary efficacy endpoint is the. success or failure, at 12 months after the final treatment intake. The patient's treatment will be a success if there is no evidence of trypanosomes in any bodily fluid, and the WBC count in the CSF is $\leq 20/\mu$ L. Patients with no parasitological evidence of relapse, but with a CSF WBC count > 20/µL or who, in the opinion of the Investigator, require rescue treatment, will be considered to be probable relapses and therefore as failures. Death due to any cause or use of rescue medication will be considered as a relapse, i.e. a failure. A patient who attends the follow-up visit at 12 months or later and who

refuses to undergo lumbar puncture, but who has no signs or symptoms of HAT and for whom the outcome was assessed as favourable at the last assessment will be considered as a probable cure, i.e. a success, unless signs of relapse are detected on any assessment up to 18 months.

Primary Analysis

The primary analysis will be performed on the ITT population.

The primary endpoint is the success or failure of treatment, as defined above.

The primary analysis of success or failure will be performed at 12 months of follow-up.

The primary test is an exact test derived from the exact confidence interval (CI) of the success rate at 12 months.

Two sets of statistical hypotheses will be tested simultaneously:

 H_{0A} : the true success rate is equal to or less than 80%, which is considered to be unacceptable.

H_{1A}: the true success rate is greater than 80%.

 H_{0B} : the true success rate is equal to or greater than 92%, which is the target or expected success rate for fexinidazole.

H_{1B}: the true success rate is less than 92%.

If H_{0A} is rejected, then the success rate is significantly greater than 80% and the estimated rate is consistent with a rate of 92%. In this case, H_{0B} is automatically accepted, but not necessarily true.

If H_{0B} is rejected, then the success rate is significantly less than the target of 92%, and the estimated rate is consistent with the unacceptable rate of 80%. In this case, H_{0A} is automatically accepted, but not necessarily true.

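### The Cochran Q-test across all visits is close to certain to be significant at the target success rate, because success can essentially only fall; a month-12-to-18 relapse proportion would tell more

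*Protocol*

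**What the plan says.** Protocol section 2.1.2 lists as a secondary objective "To study changes in the success rate over time". The matching endpoint in section 2.2.2 is "Result (success or failure) at each visit from the end of treatment to month 18". Section 9.8.3 plans a Kaplan-Meier estimate of definitive failure, visit-by-visit success rates "compared using a Cochran Q-test", and a repeated-measures logistic model that tests the time effect adjusted for centre. It also plans an analysis of success at month 18.

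Three other provisions bear on how these tests behave:

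- **Failure is lasting.** Section 5.9 gives rescue treatment on relapse or probable relapse at any time in follow-up. Section 9.8.1 adds: "Death due to any cause or use of rescue medication will be considered as a relapse", that is, a failure.
- **The CSF criterion starts late.** In Table 1 (section 5.9), success at end of treatment and at month 3 has no CSF white-cell limit, and month 3 has "no lumbar puncture at 3 months unless Investigator suspects a relapse". A limit of 20/µL appears at months 6, 12 and 18.
- **The case for month 12.** Section 2.2.1 justifies the 12-month endpoint with historical data: "the overall relapse rate between 12 and 18 months after the EOT is around 1.2" per cent.

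**The concern.** A test of equal success at all visits is informative when the rate could move either way or stay level. Here a child who has died or been rescued stays a failure, so the rate can level off or fall but hardly rise. Equality across visits then amounts to saying that nobody failed after end of treatment, which the protocol does not expect. The p-value would be reported as evidence on a stated secondary objective while saying little beyond the fact that failures occurred.

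A second issue adds to this. The first routine CSF count after treatment is at month 6 for most children (section 6.3.1 limits CSF testing at end of treatment to the first 30 unless one of them fails). Part of any fall from month 3 to month 6 may reflect that count being taken for the first time.

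**Working it through.** **Plan's own figures.** The protocol gives none for the Q-test. Its nearest figure is for the primary test (section 9.1: n = 125, 80% against 92%, one-sided 0.025, power 97.5%). With the rule of at least 109 successes, the exact binomial gives type-I error 0.0243 and power 0.978, so the sample-size figure is reproduced.

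**Inputs.** n = 125 (section 9.1: "The sample size should not be less than 125"); target 92% at 12 months (section 9.8.1); relapse of about 1.2% from month 12 to 18 (section 2.2.1). Assumed, because not stated: five visits (end of treatment, months 3, 6, 12 and 18), level 0.05, chi-square reference, no return from failure to success.

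**Formula.** With k visits, column totals C, row totals R and grand total T:

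Q = (k−1)[k·ΣC² − T²] / [k·T − ΣR²], on k−1 degrees of freedom.

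Children with the same result at every visit cancel out, so only those who change matter. For 4 degrees of freedom, p = exp(−Q/2)·(1 + Q/2).

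**Three children first failing at month 6.** Each has the row (1,1,0,0,0). C = (3,3,0,0,0), ΣC² = 18, T = 6, ΣR² = 12. Q = 4(90 − 36)/(30 − 12) = 12.0; p = e⁻⁶·7 = 0.017.

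**Other small patterns (five visits):**

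| First failures | Q | p |
|---|---|---|
| 2 at month 6 | 8.0 | 0.092 |
| 3 at any single later visit | 12.0 | 0.017 |
| 2 at month 6, 1 at month 12 | 10.2 | 0.037 |
| 2 at month 6, 1 at month 18 | 9.0 | 0.061 |
| 1 each at months 3, 6, 12 | 8.5 | 0.075 |
| 1 each at months 3, 6, 12, 18 | 10.0 | 0.040 |

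**At the target rate.** 125 × 0.08 = 10 failures by month 12, and 115 × 0.012 ≈ 1 more by month 18. Two illustrative timings over months 3, 6, 12 and 18:

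- (0, 5, 5, 1): C = (11,11,6,1,0), ΣC² = 279, T = 29, ΣR² = 81; Q = 4(1395 − 841)/(145 − 81) = 34.6, p < 0.000001.
- (2, 4, 4, 1): C = (11,9,5,1,0), ΣC² = 228, T = 26, ΣR² = 70; Q = 4(1140 − 676)/(130 − 70) = 30.9, p = 0.000003.

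**Simulated chance of p < 0.05** (20,000 trials each; the split over visits is assumed):

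| Success at month 12 → month 18 | Chance of significance |
|---|---|
| 92% → 90.8%, two different splits | 99.8% and 99.9% |
| 97% → 95.8% | 81% |
| 98.5% → 97.3% | 51% |

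**The alternative quantity.** With 125 × 0.92 = 115 successes at month 12 and one later relapse, the proportion is 1/115 = 0.9%, Clopper-Pearson 95% interval 0.02% to 4.8%. It can be set directly beside 1.2%.

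**The case against.** The Q-test is a standard paired test for binary outcomes, its null matches the wording of the objective, and rejecting when success has fallen is not an error. That stands: nothing here shows an inflated type-I error. The weakness is that the answer is almost known in advance.

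Several stronger readings are tempting, and the documents do not support them.

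- *Any three failures make the test significant.* They must fall at the same or nearly the same visit. With four visits (dropping either end of treatment or month 3), three at month 6 give a chi-square p of 0.029 but an exact p of 0.0625. If one of the three returned to success, p would be 0.061; such a return is possible if a raised month-6 count were scored as failure without rescue.
- *Refusers of lumbar puncture count as successes only at month 18.* Table 1 does list at month 18 a "Patient with no signs of HAT who refuses to undergo lumbar puncture", but sections 2.2.1, 9.2 and 9.8.1 also accept refusers at month 12 under conditions. The clearer Table 1 difference is that a count above 20/µL can be a probable success at month 12 but is a probable failure at month 18.
- *A fall at month 6 is produced by the definition.* Table 1 is a clinical-management table, and the analysis definition is written out only for month 12, so scoring at other visits may be settled in the analysis plan. The schedule still provides no routine CSF count at month 3, so the possibility remains, but only as a possibility.

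It is also fair that most of the remedy is already planned (Kaplan-Meier, visit rates, month-18 success), and that the protocol rests the choice of month 12 on historical data, not on this test.

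**Conclusion.** The point holds in a limited form. With failure essentially lasting, the all-visit Q-test can favour its null only if almost no child fails after end of treatment. At the protocol's target rate, significance is nearly certain and carries little information. The size is firm at that rate and weaker if efficacy is much better (about 81% at 97% success, 51% at 98.5%). The small-count figures rest on five visits, a 0.05 level and the chi-square reference.

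The repeated-measures time test uses the same visit outcomes and asks the same question of them, so the same caution applies. No figure was computed for it.

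A reader might infer that the trial's conclusion is at risk. It is not: the success criterion in section 9.8.1 uses month 12 alone. This is a minor improvement to a secondary analysis.

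**What to change.** 1. Do not use the all-visit Q-test, or the all-visit time-effect p-value, as evidence on change over time.
2. Report the planned Kaplan-Meier estimate and the visit success rates with confidence intervals at months 6, 12 and 18.
3. Add the proportion of children with an observed month-12 success who fail by month 18, with an exact 95% interval, beside the historical 1.2%.
4. Score both visits by the single section 9.8.1 definition (CSF white cells at most 20/µL, the same rule for refusers), not by the Table 1 bands. Otherwise a child with an unchanged count above 20/µL could move from probable success to probable failure by definition alone.
5. Take month-12 status from that visit. Sections 2.2.1 and 9.8.1 let later findings override some month-12 outcomes, which could remove relapses from the very interval being measured.

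The cost is analysis wording and one planned p-value. The new interval will be wide: in the example its upper limit of 4.8% is four times 1.2%. It describes relapse from month 12 to 18 but cannot by itself prove that month 12 predicts month 18.
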